#### 3.5.2. Laboratory Data

Using the current Pfizer data standards, the last pre-dose value is used as the baseline for all laboratory parameters.

#### 3.5.3. Vitals and ECGs

Baseline values for vital signs and ECG will be the last completed pre-dose measurement.

If not supplied, QTcF will be derived using Fridericia's heart rate correction formula:  $QTcF = QT / (RR)^{(1/3)}$ , where  $RR = 60/HR$  (if  $RR$  is not provided).

### 4. ANALYSIS SETS

Data for all subjects will be assessed to determine if subjects meet the criteria for inclusion in each analysis population prior to unblinding and releasing the database and classifications will be documented per standard operating procedures.

#### 4.1. Full Analysis Set

The Full Analysis Set (FAS) is defined as all subjects randomized and who have received at least one dose of randomized treatment. All the efficacy endpoints analyses will be conducted using FAS.

090177e1909dd632\Approved\Approved On: 25-Mar-2019 05:54 (GMT)

## **4.2. Per Protocol Analysis Set**

The Per Protocol Analysis Set (PPAS) will be a subset of the FAS dataset. Subjects may be excluded from the PPAS if they did not meet all eligibility criteria, experienced dosing interruptions, had changes to their steroid medications or regimen, or did not complete through week 49.

Exclusions from the PPAS will be reviewed in a blinded fashion and reasons for excluding subjects from the PPAS and subject numbers excluded will be documented and forwarded to programming prior to database being unblinded.

## **4.3. Safety Analysis Set**

The Safety Analysis Set is defined as all subjects who receive at least 1 dose of investigational drug.

## **4.4. Other Analysis Sets**

### **4.4.1. PK Concentration Analysis Set**

The PK concentration population is defined as all enrolled subjects who received at least 1 dose of PF-06252616 and in whom at least 1 concentration value is reported.

### **4.4.2. PK Parameter Analysis Set**

The PK parameter analysis population is defined as all enrolled subjects who received at least 1 dose of PF-06252616 and in whom at least 1 of the PK parameters of interest is calculated.

### **4.4.3. GDF-8 Concentration Analysis Set**

The GDF-8 concentration population is defined as all enrolled subjects in whom at least 1 GDF-8 concentration value is reported.

### **4.4.4. GDF-8 Parameter Analysis Set**

The GDF-8 parameter analysis population is defined as all enrolled subjects in whom at least 1 of the GDF-8 parameters of interest is reported.

## **4.5. Treatment Misallocations**

If a subject was:

- Randomized but not treated, then they will be reported under their randomized treatment group for efficacy analyses. However, they are by definition excluded from the safety analyses as actual treatment is missing.
- Treated but not randomized, then by definition they will be excluded from the efficacy analyses since randomized treatment is missing, but will be reported under the treatment they actually received for all safety analyses.

- Randomized but took incorrect treatment, then they will be reported under their randomized treatment group for all efficacy analyses, but will be reported under the treatment they actually received for all safety analyses.

**4.6. Protocol Deviations**

The method used to identify the PPAS is defined in the table below. The clinician will review blinded listings of source-verified data from the database prior to unblinding and database release to assess subject eligibility.

Following assessment of the data for all subjects, the project statistician will ensure that the list of subjects and the reason for exclusion is clearly documented. This list should be approved by the clinician and forwarded by the statistician to the clinical programmer for inclusion in the final analyses and Clinical Study Report (CSR) tables.

**Table 2. Potential Exclusions from the PPAS**

Reasons for Subject Exclusion	Responsible	Action/Source	Required Listings from Programming
Eligibility Criteria	Programming/Clinical	Programming review list of inclusion/exclusion criteria not met Clinical reviews before excluding subjects from population	Inclusion and Exclusion
Dosing Interruptions	Programming/Clinical	Programming checks for interruptions to the dosing schedule and sends to clinical for review	Dosing Information
Steroid Medication Changes	Clinical	Clinical reviews concomitant medication listing of steroids	Concomitant Medications, Glucocorticoids
Insufficient Follow-up	Programming	Subjects who discontinue before week 49 will be excluded based on programmatic review of discontinuations	
Other Possible Exclusions	Clinical	Review protocol deviations for lack of protocol adherence	Study protocol deviations log

Subjects may be excluded from the PPAS if they did not meet all eligibility criteria, experienced dosing interruptions, had changes to their steroid medications or regimen, did not complete through week 49, or other protocol deviations as supported by adequate justification and documentation.

090177e1909dd632\Approved\Approved On: 25-Mar-2019 05:54 (GMT)

## 5. GENERAL METHODOLOGY AND CONVENTIONS

### 5.1. Hypotheses and Decision Rules

The assumed null and alternative hypotheses for testing the active treatment versus the placebo on the 4 stair climb are included below:

$$H_0: (\mu_{\text{active, 49 weeks}} - \mu_{\text{active, baseline}}) - (\mu_{\text{placebo, 49 weeks}} - \mu_{\text{placebo, baseline}}) = 0$$

$$H_1: (\mu_{\text{active, 49 weeks}} - \mu_{\text{active, baseline}}) - (\mu_{\text{placebo, 49 weeks}} - \mu_{\text{placebo, baseline}}) > 0$$

The primary efficacy analysis will be tested at  $\alpha=0.025$  (one-sided). The same type 1 error rate will be used for testing the secondary analyses. This test will be performed based on the data in period 1 from all subjects. Subjects assigned to sequence 1 and sequence 2 will be analyzed together in an active treatment group compared to subjects in sequence 3 (placebo during period 1).

The decision criteria for the interim analysis is described in CCI

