### 1.10. Study Design Rationale

The four stair climb (4SC) has been selected as the primary endpoint for this study based on results of prior oral steroid clinical trials in DMD. The 4SC has been measured for more than 20 years in DMD, widely used as an outcome in clinical trials, deemed as a reliable measure of motor function (Bushby et al 2011; McDonald et al 2013), can be “bench-marked” by a meaningful improvement with steroids (Manzur et al, 2008) and is a meaningful indicator of DMD boys’ lower limb function in a one year study.

Oral steroids are the only treatment demonstrated in randomized controlled trials to improve DMD boys’ strength and function. (Griggs et al 1991; Mendell et al, 1989). Functional improvements were measured as the time required to walk or run 9 meters or to climb 4 stairs after six months of daily steroids. In a pooled analysis of three separate steroid studies, the magnitude of six month functional improvement compared to placebo group was larger as measured by the stair climb test (-3.69 sec 95% CI [-4.71 to -2.67 sec]) than the walk/run test (-2.64 sec 95% CI [-3.70 to -1.58]) (Manzur et al, 2008). Clinically, propelling oneself up stairs requires more proximal leg strength than walking on a flat surface. This is supported by the natural history of DMD in that boys lose the ability to climb stairs prior to the loss of ambulation (Bushby et al, 2011; McDonald et al, 1995). In addition, there is data to support that a prolonged 4SC >8 seconds time is associated with loss of ambulation in 12 months (McDonald et al, 2013). There is a stronger correlation between knee extensor strength, a key lower limb muscle to maintain ambulation, and 4SC ( $r=0.74$ ) than time to walk/run ( $r=0.70$ ) and distance walked in six minutes ( $r=0.64$ ) (McDonald et al, 2013). A recent industry sponsored trial from PTC Therapeutics (placebo group) demonstrated that DMD boys treated with steroids and  $\geq 7$  years of age demonstrated a mean change of 4.7 sec  $\pm 7.5$  sec over 12 months (McDonald et al, 2013). Therefore, ability to improve time to climb 4 stairs in a 12 month study while boys receive standard of care steroid treatment is a pertinent functional endpoint.

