### **7.8.2. 4 Stair Climb (4 SC)**

The primary efficacy endpoint will be based on the 4 SC (with or without the use of hand rails). The 4 SC quantifies in seconds the time required for a subject to ascend 4 standard steps. The method the subject uses (eg, using the hand rails) to climb the stairs is recorded to understand any change in technique that occurs over time, however at no time is the subject instructed on the preferred method (with or without the use of hand rails) used to perform this test.

Subjects will also be assessed on the time to descend 4 stairs. The methods used to descend 4 stairs will also be recorded.

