#### **9.1. Sample Size Determination**

The sample size is based on the primary endpoint of demonstrating efficacy of change from baseline on a 4 stair climb timed function test as compared to placebo at 49 weeks. To detect a 2.5 second difference in change from baseline in 4 stair climb based on a difference between the active treatment and the placebo treatment in Period 1 assuming a common

standard deviation of 4.0 with 80% power at  $\alpha=0.05$  (two-sided), a 2:1 treatment allocation and one interim analysis a total of 96 subjects should complete 49 weeks of dosing for this assessment. Assuming a 10% attrition rate, approximately 105 subjects should be enrolled (70 subjects receiving PF-06252616 and 35 subjects receiving placebo) in order to ensure sufficient number of subjects will complete this assessment. If there are no safety issues and enrollment has completed, additional subjects may be enrolled prior to the time of the interim analysis. These additional subjects may help off-set any unforeseen variability that may occur outside the presumed standard deviation for this age group.

One interim analysis is planned to evaluate futility and efficacy after approximately 50% of the subjects have completed through Week 49. Alpha- and beta-spending functions will be used to determine the cutoffs for efficacy and futility at the interim based on the observed number of subjects in the interim analysis. The gamma family spending functions will be used to appropriately account for error spending and adjust for the observed information at the time of the interim analysis and conservative boundaries ( $\gamma \leq -1$ ) will be used to define the futility and efficacy boundaries. The cutoff used at the interim analysis will be calculated based on the percentage of subjects included at the interim analysis to ensure appropriate protection of the type I error. Further details regarding the interim analysis and simulations are included in the SAP.

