### **5.3. Methods to Manage Missing Data**

*Missing data will be handled using maximum likelihood techniques for a mixed effects model, also called a mixed-effect model for repeated measures(MMRM). This analysis is unbiased under the assumption of missing at random when the model assumptions hold. Subjects who lose the ability to complete a functional assessment and/or ambulate will be assumed to be missing not at random. Additional imputation methods to assess the sensitivity of the analysis to missing not at random data will also be performed. The methods include transforming time to complete a functional assessment to velocity, so that subjects with a missing time will be assumed to have a velocity of zero.*

Missing data for the PODCI patient reported outcome will be handled according to the guidance of the developers.

Values below the limit of quantification will be analyzed at the limit of quantification for that parameter except for PK data (see [Section 6.3.1.1](#)). For laboratory listings, the <BLQ will be used with the actual limit of quantification in place of BLQ.

For the primary endpoint analysis, ie, change from baseline to Week 49 on 4SC time, if there are >10% subjects who discontinue treatment before Week 49, then additional sensitivity analysis using ANCOVA model (or Wilcoxon test in case of rejection of normality of ANCOVA residuals) will be conducted and using the following two methods for handling the missing data:

- Jump-to-control with multiple imputation.
  - Assume subjects in active treatment group who discontinue treatment behave on average like control (placebo) group after discontinuation.
  - Implement using multiple imputation to get variability estimates.
- Tipping point analysis: In case the primary efficacy test using completers-only data is statistically significant, increase penalty for active treatment while having no penalty for placebo group, until the result is no longer statistically significant.

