## 6. ANALYSES AND SUMMARIES

### 6.1. Primary Endpoint

#### 6.1.1. Primary Analysis

The primary endpoint, change from baseline in 4 stair climb, will be analyzed based on the FAS using the mixed effects model outlined in [Section 5.2](#). For primary efficacy analysis, besides FAS, PPAS will be used to assess the sensitivity of the analysis results. These analyses will be performed based on the data for all subjects through 49 weeks. Subjects in sequence 1 and 2 will be combined for analysis purposes and compared to the placebo subjects in sequence 3. Covariates for this analysis include the time to climb 4 stairs at baseline, treatment, visit and treatment by visit interaction. Model estimates and change from placebo estimates, 95% two-sided confidence intervals, and p-values will be displayed for study interpretation purposes. Model estimates with confidence intervals will also be displayed graphically. Graphical summaries of the raw data, including boxplots, will be created to highlight outliers and other influential observations.

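### SAP 5.1 prints the one-sided alternative for 4 stair climb time in the direction of harm: active minus placebo change above zero means slower climbing on active.

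*SAP*

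**What the plan says.** SAP 5.1 (Hypotheses and Decision Rules) introduces its hypotheses with "The assumed null and alternative hypotheses for testing the active treatment versus the placebo on the 4 stair climb are included below". The null is a zero difference in change from baseline to Week 49; the alternative is "H_1: (\mu_{\text{active, 49 weeks}} - \mu_{\text{active, baseline}}) - (\mu_{\text{placebo, 49 weeks}} - \mu_{\text{placebo, baseline}}) > 0". The test is one-sided at 0.025, with Sequences 1 and 2 pooled as active and compared with Sequence 3. Only the type 1 error rate, not the inequality, is carried over to the secondary analyses.

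The scale and the direction of benefit are fixed elsewhere:

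- Protocol 7.8.2: "The 4 SC quantifies in seconds the time required for a subject to ascend 4 standard steps".
- SAP 5.3: "For the primary endpoint analysis, ie, change from baseline to Week 49 on 4SC time". SAP 6.1.2 uses velocity, the reciprocal of time, only as a sensitivity analysis.
- Protocol 1.10, on the pooled steroid trials: "functional improvement compared to placebo group was larger as measured by the stair climb test (-3.69 sec 95% CI". Improvement is therefore a negative difference. The same section gives a placebo-group change of 4.7 s over 12 months, so decline is positive.

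Three other statements bear on the test:

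- SAP 5.3, tipping-point analysis of a significant result: "increase penalty for active treatment while having no penalty for placebo group, until the result is no longer statistically significant".
- SAP 6.1.1: "Model estimates and change from placebo estimates, 95% two-sided confidence intervals, and p-values will be displayed for study interpretation purposes".
- Protocol 9.1 sizes the trial at alpha 0.05: "two-sided), a 2:1 treatment allocation and one interim analysis a total of 96 subjects should complete 49 weeks of dosing".

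**The concern.** On a time scale, the alternative in SAP 5.1 says that active-treated boys slow down more than placebo boys. The objective is to demonstrate efficacy, so the rejection region lies on the wrong side of zero.

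SAP 5.1 is the only readable text that sets the one-sided rejection direction for the primary test. If a program follows it literally, a clear benefit yields a p-value near 1 and a clear harm yields a claim of efficacy. If the programmers silently correct it, the primary decision rule actually used differs from the approved one, and someone may have to explain after unblinding why the rule was read the other way.

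**Working it through.** **1. Direction.** SAP 5.1 writes Week 49 minus baseline within each arm, then active minus placebo. With 4SC in seconds, a drug that slows decline gives a negative value, and so does one that speeds climbing. The printed sign would suit velocity, but the primary analysis is on time. No readable text redefines change as baseline minus Week 49.

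**2. The plan's sample size.** Inputs from Protocol 9.1: difference 2.5 s, SD 4.0, 80% power, two-sided 0.05, 2:1 allocation, one interim analysis, 96 completers.

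- Fixed design: placebo n = (1.960 + 0.842)² × 4.0² × (1 + 1/2) / 2.5² = 30.14, so the total is 3 × 30.14 = 90.4, or 31 + 62 = 93 after rounding up. One-sided 0.025 gives the same number.
- Adding one look at 50% information with gamma-family spending and non-binding futility: with gamma = -2 for both boundaries, the inflation is 1.063 and the total 96.1. The documents state only gamma ≤ -1, so -2 is an assumption; gamma from -1 to -8 gives about 90 to 100.

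The stated 96 is reproduced and does not depend on the sign.

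**3. The printed rule at the planned effect.** With 64 active and 32 placebo completers, SE = 4.0 × √(1/64 + 1/32) = 0.866 s, and 2.5 / 0.866 = 2.887.

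| True difference (active minus placebo) | Reject under H1 > 0 (printed) | Reject under H1 < 0 |
|---|---|---|
| -2.5 s (benefit) | Φ(-1.960 - 2.887) = 6.3e-7 | 0.823 |
| 0 | 0.025 | 0.025 |
| +2.5 s (harm) | Φ(2.887 - 1.960) = 0.823 | 6.3e-7 |

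At an observed -2.5 s (z = -2.887), the upper-tail p-value is 0.998 and the lower-tail p-value 0.002. The protocol's two-sided 0.05 test has power 0.823 at either -2.5 s or +2.5 s.

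**4. With the interim look.** Alpha spent at information t = 0.5 is 0.025 × (1 - e^(-γt)) / (1 - e^(-γ)). Only the efficacy bound is applied, and gamma is assumed.

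| Gamma | Bounds (interim, final) | Printed rule at 2.5 s benefit | Printed rule at 2.5 s harm |
|---|---|---|---|
| -1 | 2.348, 2.066 | 6.0e-6 | 0.804 |
| -4 | 2.750, 1.981 | 1.4e-6 | 0.819 |

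By symmetry, the corrected rule has power 0.80 to 0.82 at the planned benefit, in line with the protocol's 80%.

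**5. The tipping-point rule.** Treat the penalty as a shift in the active mean with the SE unchanged; SAP 5.3 does not specify its form.

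- H1 < 0, starting at -2.5 s: significance needs a difference beyond 1.986 × 0.866 = 1.72 s (t, 94 df), so a penalty of 2.5 - 1.72 = 0.78 s removes it (0.80 s with 1.960).
- H1 > 0, starting from a significant +2.5 s (z = 2.89): a 1 s penalty gives (2.5 + 1) / 0.866 = 4.04, and 2 s gives 5.20. The result moves away from the boundary and never tips.

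The rule works only when significance favours active.

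**The case against.** The strongest reply is that this is a typographical slip with no practical consequence. The point turns on one character in an equation that a program read from PDF. The interim decision section is redacted, including a table of decision probabilities by true difference, and it may fix the direction properly. One-sided 0.025 and two-sided 0.05 share the critical value 1.96 and give the same sample size, so sidedness alone is no error. The efficacy objective, the negative steroid benchmark, the two-sided displays and the tipping-point rule all show what was meant, so the sign can be settled before unblinding. The rejection probabilities above describe an analysis that nobody would run on purpose.

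Much of this stands. The printed sign must be checked against the source page. Nothing can be said about the interim boundaries. The conflict with the protocol is not about alpha: the printed one-sided alternative discards the tail where benefit lies. The probabilities show what the line says if followed literally; they do not predict what will happen.

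It does not rescue the line itself. That the rest of the plan shows the opposite intention is the evidence that SAP 5.1 is wrong. A primary decision rule should be correct where it is stated, not inferred from other sections.

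**Conclusion.** The concern holds. As the text reads, the primary alternative in SAP 5.1 has the wrong sign for 4SC time, and this should be fixed. Read literally, it gives essentially no chance of success at the planned 2.5 s benefit (6.3e-7 fixed; 1.4e-6 to 6.0e-6 with one look) and a chance of about 0.80 to 0.82 of rejecting in favour of the stated alternative at a 2.5 s harm.

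These figures rest on the protocol's SD of 4.0, a 64/32 split of the 96 completers, a two-sample comparison in place of the mixed model and, for the look, 50% information with an assumed gamma of -1 to -4 and no futility stopping. The direction of the error depends on none of these; it depends only on the inequality having been extracted correctly. The finding is confined to the 4SC hypothesis.

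**What to change.** In SAP 5.1, make one of these changes:

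- write the alternative as below zero for active minus placebo change in 4SC time;
- keep the inequality and reverse the subtraction; or
- replace it with the protocol's two-sided 0.05 test and define benefit as a negative difference.

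Add a sentence saying that a shorter time is better. Check the printed sign against the source PDF first. Confirm that the final analysis program and the interim efficacy and futility programs use the same sign convention. Stating the direction of benefit for each secondary endpoint would be a useful clarification but is not part of this error.

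The cost is one line of SAP wording and a program check, with no change to design, model, sample size, data collection or patients.

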#### 7.8.5. Strength Assessment

Muscle strength will be quantified by means of a handheld dynamometer. The following muscle groups will be evaluated: knee extension, elbow flexion, elbow extension and shoulder abduction.

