### 9.2.3. Analysis of the Exploratory Endpoints

All exploratory endpoints, including the pharmacologic and health outcome endpoints, will be summarized by treatment group and period. Additional analyses may be performed to understand the relationship between these endpoints and treatment. Analyses of the primary and secondary endpoints during Period 2 will be considered exploratory. These endpoints will be summarized by period and additional analyses may be performed.

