#### 3.2. Secondary Endpoints

- *Mean change from baseline as compared to placebo on function tests including, Forced Vital Capacity (FVC), Northstar Ambulatory Assessment (NSAA), range of motion (ROM), Performance of Upper Limb (PUL), 6MWD at Week 17, 33, and 49.*
- *Mean change from baseline as compared to placebo on the 4SC at Week 17 and 33.*
- *Mean change from baseline as compared to placebo on muscle strength by myometry at Week 17, 33, and 49.*
- *In subjects randomized to Sequence 1, mean change from baseline as compared to historical control (see [Section 6.2.1](#)) on functional tests including, 4SC, 6MWD, FVC, NSAA at week 97.*
- *In the pre-specified subset of subjects who have baseline 4SC <3.5 seconds, ≥3.5 seconds and ≤8 seconds, or >8 seconds, the mean change from baseline as compared to placebo on muscle strength by myometry and on function tests including, 4SC, FVC, NSAA, PUL, 6MWD at Week 17, 33 and 49.*

Within the Northstar Ambulatory Assessment (NSAA), the two timed function tests, Rise from Floor and Run 10 meters will be analyzed separately for summary tabulation along with the total NSAA score.

The forced vital capacity(FVC) has been collected as the best 3 values at each of the given visits. Only the single best value (maximum forced vital capacity) will be used to analyze the FVC assessment. The percent predicted FVC is provided on the case report form from the best FVC value.

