## 6.2. Secondary Endpoints

*Secondary endpoints of change from baseline at Weeks 17, 33, and 49 in FVC, Northstar Ambulatory Assessment (including time to stand and 10 meter walk/run), ROM, PUL, 6MWD, myometry based strength assessments, and MRI muscle volume (including mean percent change in Whole Thigh Muscle Volume and in Whole Thigh Muscle Volume Index defined in [Section 3.3.2](#)) endpoints will be analyzed using the same longitudinal mixed model as described for the primary analysis. Transformation of the data will also be considered if model assumptions are not met. These analyses will be based on the FAS. Analyses using PPAS may be explored to assess the sensitivity of analysis results. The baseline stratification factor will be included in the model along with the other effects described in [Section 6.1.1](#). For the MRI endpoints of Whole Thigh Muscle Volume and Whole Thigh Muscle Volume Index, baseline age may be included as an additional covariate, if needed, to account for growth. If a high degree of collinearity is observed between the baseline value for other time function tests and the stratification factor, the baseline time for the functional test of interest will remain in the model. The same model estimates and graphical displays will be created for the secondary analyses as described in [Section 6.1.1](#).*

*Additionally, a sensitivity analysis based on velocity may also be performed as described for the primary analysis for other timed function tests.*

For the change from baseline to Week 97 in 4SC, 6MWD, FVC, NSAA, the subjects randomized to Sequence 1 will be compared against the historical control group (see [Section 6.2.1](#)) using the same statistical analysis methods as described earlier for the primary and secondary analyses.

In the pre-specified subset of subjects who have baseline 4SC <3.5 seconds,  $\geq 3.5$  seconds and  $\leq 8$  seconds, or >8 seconds, changes from baseline as compared to placebo on muscle strength by myometry, on MRI muscle volume, and on function tests including, 4SC, FVC, NSAA, PUL, 6MWD at Week 17, 33 and 49 will be analyzed using the same statistical methods as described earlier for the primary and secondary analyses.

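### SAP 5.1 tests each Period 1 secondary analysis at one-sided 0.025 with no order, gate on the primary or nominal label, so 0.025 is only a per-comparison error rate

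*SAP*

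**What the plan says.** SAP 5.1 (Hypotheses and Decision Rules) states one null hypothesis, for 4SC at Week 49, with Sequences 1 and 2 pooled against Sequence 3. It assigns one-sided 0.025 to that test and continues: "The same type 1 error rate will be used for testing the secondary analyses". The sentences that follow limit the testing to Period 1 data.

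SAP 3.2 lists the secondary endpoints. In all boys these are:
- FVC, NSAA, ROM, PUL and 6MWD at three visits;
- 4SC at Weeks 17 and 33;
- strength: "Mean change from baseline as compared to placebo on muscle strength by myometry at Week 17, 33, and 49".

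SAP 3.2 also says that the two timed NSAA items are analysed separately. Protocol 7.8.5 names the muscle groups measured: "knee extension, elbow flexion, elbow extension and shoulder abduction". SAP 6.2 adds thigh muscle volume and its index to the secondary models.

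On output, SAP 6.2 says: "The same model estimates and graphical displays will be created for the secondary analyses as described in" Section 6.1.1. That section specifies "95% two-sided confidence intervals, and p-values will be displayed for study interpretation purposes".

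Two nearby statements limit other analyses but not these. SAP 6.6.1 disclaims multiplicity adjustment, for adverse events only. Protocol 9.2.3 says: "Analyses of the primary and secondary endpoints during Period 2 will be considered exploratory". Neither covers the Week 17, 33 and 49 comparisons.

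**The concern.** The sentence in SAP 5.1 is a stated testing rule, in the section that holds the decision rules. It gives every secondary comparison the primary's full error rate and sets no condition. A report that followed it could call a secondary result significant at 0.025 whether or not 4SC succeeded, with many chances to do so.

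Failure of the primary is a realistic case. The SAP version history (version 2 row) reports newer natural-history data with a one-year 4SC change of 0.9 to 1.99 seconds, against about 2.9 seconds assumed when the protocol was written. Those data come from boys aged 6 to under 10, a narrower range than the trial's. Protocol 9.1 still sizes the study "To detect a 2.5 second difference in change from baseline in 4 stair climb". If 4SC proves uninformative, interpretation will lean on the secondaries, where the error rate is not controlled.

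**Working it through.** **1. The plan's own figure.** The documents state no error rate for the secondary set. The related figure is the 96 completers in Protocol 9.1 (difference 2.5 s, SD 4.0 s, 80% power, two-sided 0.05, 2:1 allocation, one interim).
- Without an interim: n(placebo) = (1.960 + 0.842)² × 4.0² × (1 + 1/2) / 2.5² = 30.1, so 31, and 93 in total.
- With one look at 50% information, gamma-family spending with gamma = −1 and no power lost to futility: N = 95.1, so 96.

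The figure reproduces. Two-sided 0.05 in the protocol and one-sided 0.025 in the SAP are the same level for the primary, so nothing is wrong there.

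**2. Counting the tests (Period 1, all boys).**
- Week 49 measures in SAP 3.2: FVC, NSAA, ROM, PUL, 6MWD, myometry = **6**.
- All Period 1 tests in SAP 3.2: 5 × 3 visits + 4SC × 2 + myometry × 3 = **20**.
- Widest count: (5 function measures + 2 NSAA timed items) × 3 = 21; 4SC × 2 = 2; four muscle groups × 3 = 12; thigh muscle volume and index × 3 = 6. Total **41**.

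The baseline-4SC subsets in SAP 3.2 and 6.4 and the Week 97 comparison are left out of all three counts.

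**3. Formula.** Assume the drug has no effect on any endpoint. For m one-sided tests at 0.025 with equal correlation ρ, the chance of at least one false positive is

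1 − ∫ φ(z) · Φ((1.96 − √ρ·z)/√(1−ρ))^m dz,

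which is 1 − 0.975^m when ρ = 0. The documents give no correlations, so ρ is an assumption and is shown over a range.

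| Tests | ρ = 0 | ρ = 0.5 | ρ = 0.8 |
|---|---|---|---|
| 6 | 14.1% | 10.4% | 6.9% |
| 20 | 39.7% | 21.0% | 11.2% |
| 41 | 64.6% | 29.1% | 14.1% |

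Against 2.5%, the smallest entry is 6.9/2.5 = 2.8 times and the largest 64.6/2.5 = 25.8 times. The expected number of false positives is m × 0.025: 0.15, 0.5 and about 1.0.

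**4. Cross-check with another correlation structure.** The 20 tests were simulated with correlation 0.3 to 0.7 between endpoints and 0.6 to 0.8 between adjacent visits, decaying with distance. This gives 28.7% down to 16.5%, inside the 20-test range above.

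**5. Effect of a gate.** In the same simulations, requiring the primary to succeed first brings the chance of any claimable secondary to 1.6–2.2% when nothing works. That does not cover the case where the primary is truly non-null and there is an interim look. Suppose a null secondary is tested at full 0.025 at whichever look the primary crosses. With 50% information, gamma = −1 (boundaries 2.348 and 2.066) and a secondary perfectly correlated with the primary, the worst-case one-sided secondary error is about 4.1%. A gate therefore has to say how the looks are handled.

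**The case against.** The strongest reply is that this is a Phase 2 study whose secondary objectives are worded as characterising or evaluating, while only the primary efficacy objective is to demonstrate. Neither document promises family-wise control for secondaries, so 0.025 can be read as a per-comparison level. That reading is fair and keeps the point moderate. But the wording of the objectives is not a nominal label, and it conflicts with a sentence that assigns a testing error rate.

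The count can also be disputed, and this stands in part. SAP 3.2 lists myometry as one endpoint, and no passage says each muscle group is a separate test. The timed NSAA items are separated for tabulation, although SAP 6.2 also models them. Thigh volume and index are defined under SAP 3.3.2, outside the SAP 3.2 list. The 41 is therefore partly inference; 20 and 6 come straight from SAP 3.2.

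A reader might infer more than the documents support:
- **That the Week 97 historical-control comparison is also tested at 0.025.** SAP 3.2 lists it as secondary, but SAP 5.1 confines the testing to Period 1, and Protocol 9.2.3 calls Period 2 analyses exploratory. SAP 6.3 does not repeat that protocol sentence, but this does not revoke it.
- **That the drug could advance on one secondary p-value.** No readable passage says so. The later interim tiers are redacted and cannot be counted either way.
- **That one error figure can be quoted.** Any single number fixes both a test count and a correlation that the documents do not supply.
- **That the primary's type I error is inflated.** It is not.

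**Conclusion.** The point holds for the Period 1 secondary analyses. SAP 5.1 tests each at one-sided 0.025 with no order, gate, split or nominal label, so a secondary could be called significant after the 4SC primary fails. Under the global null with equal correlation from 0.8 to 0, the chance of at least one false-positive secondary is about 7–14% (6 Week 49 measures), 11–40% (20 tests) or 14–65% (41 tests). These ranges rest on assumed correlations and on the counting rules above. The conclusion does not depend on which is chosen, since even the narrowest count with high correlation is well over twice the stated rate. This should be corrected, but it does not threaten the primary analysis.

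**What to change.** **Preferred.** Delete "The same type 1 error rate will be used for testing the secondary analyses" from SAP 5.1 and state that secondary p-values and confidence intervals are nominal and support no confirmatory claim. This resolves the point completely.

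**Alternative, if the sponsor wants claimable secondaries.** Name a short, sponsor-chosen fixed sequence of Week 49 endpoints, tested only if the 4SC primary succeeds. Each is tested at one-sided 0.025, stopping at the first non-significant result. Either test the sequence only at the final Week 49 analysis, or give the secondaries their own group-sequential boundaries. Label every other secondary comparison nominal.

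**Cost.** SAP wording only; no new data, patients or analyses. The downside is that fewer secondary results can be called significant: none under the preferred option, and none under the alternative if the primary fails.
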